3.5 SURGICAL GUIDELINES

Craniotomy will be performed on all subjects participating in this protocol. The surgical procedure is necessary component of clinical management. Patients will be under the care of the operating neurosurgeon of the Surgical Neurology Branch, NINDS.

3.6 COST AND COMPENSATION

3.6.1 Costs

NIH does not bill health insurance companies or participants for any research or related clinical care that participants receive at the NIH Clinical Center. If some tests and procedures performed outside the NIH Clinical Center, participants may have to pay for these costs if they are not covered by insurance company. Medicines that are not part of the study treatment will not generally be provided or paid for by the NIH Clinical Center.

3.6.2 Compensation

Participants will not be compensated on this study.

3.6.3 Reimbursement

The NCI will cover the costs of some expenses associated with protocol participation. Some of these costs may be paid directly by the NIH and some may be reimbursed to the participant/guardian as appropriate. The amount and form of these payments are determined by the NCI Travel and Lodging Reimbursement Policy.

Abbreviated Title: Phase II Study LB100 gliomas

Version Date: 06/02/2022

3.7 CRITERIA FOR REMOVAL FROM PROTOCOL THERAPY AND OFF STUDY CRITERIA

Prior to removal from study, effort must be made to have all subjects complete a safety evaluation approximately 30 days following the last dose of study therapy.

3.7.1 Criteria for removal from protocol therapy

- Completion of protocol therapy, craniotomy, PK and PD evaluations.
- Unacceptable Toxicity
- Investigator discretion
- Positive Pregnancy Test

3.7.2 Off-Study Criteria

- Screen failure
- Pathological evaluation demonstrates treatment effect (e.g. necrosis or inflammation as a result of therapy) rather than tumor recurrence, PK and PD evaluations will not be performed in these subjects. However, given presurgical exposure to LB100 patient will still be followed for AEs as noted in section **6.1**.
- Completed study follow-up period
- Participant requests to be withdrawn from study
- Loss of capacity to provide consent
- Investigator Discretion

4 CONCOMITANT MEDICATIONS/MEASURES

All participating subjects will undergo a craniotomy for resection of recurrent tumor.

Concomitant medications/measures as clinically indicated will be delivered. The surgical team will provide routine care as needed. Participation in this study will not limit any routine care.

Only those medications that the patient is taking at baseline on a routine basis or medications that cause an AE will be captured in database. Thus one time medications and PRN medications will not be captured in database except those used to treat adverse events.]

5 CORRELATIVE STUDIES FOR RESEARCH/PHARMACOKINETIC STUDIES

5.1 BIOSPECIMEN COLLECTION

5.1.1 Pharmacokinetic/Pharmacodynamic Studies

Please note that tubes and media may be substituted based on availability with the permission of the PI or laboratory investigator.

5.1.1.1 Blood

Plasma PK: Plasma sampling for PK measurements of LB100 will be performed on all participating subjects. Blood samples for the determination of plasma levels of LB-100 and its metabolite LB100 M (endothall) will be obtained from each patient via 6mL chilled sodium heparin tube (BD, Franklin Lakes, NJ). At each time point, 6 mL will be drawn into a chilled heparin collection tube and kept on ice. Blood should be processed into plasma within 30 minutes of collection. Once plasma is aliquoted, 5N sodium hydroxide (NaOH) will be added at a ratio of 1:100 relative to plasma (e.g., 0.02 mL of 5N NaOH added to 2 mL plasma); the final NaOH concentration will be 50 mM in plasma. The fortified plasma will then be aliquoted into equal volumes in cryovials and frozen at -70° C until the time of analysis. Plasma PK evaluation will be performed in the [name] Laboratory as described in **5.1.3**

Blood samples will be collected at the following time points: 1*) Pre-dose; 2*) End of infusion (2 hours post-start); 3*) 30 minutes post LB100 infusion completion; 4*) 1 hour post LB-100 infusion completion; 5*) 2 hours post LB100 infusion completion; 6) 4 hours post LB100 infusion completion; 7) 8 hours post LB100 infusion completion; 8) Other blood samplings will take place at the time post-infusion tissues are retrieved. Note: * indicates that the sample may be obtained during the operative procedure. Later time points are after leaving the OR. All blood collection specified within time is allowed for +/- 15 minutes windows, with the exception of the pre-dose sample. The pre-dose blood sample may be collected any time within 48 hours prior to drug administration. Also, blood PK is at physician discretion. The primary purpose of the study is to determine the **tissue** PK (brain tumor).

Bioanalytical measurements will be conducted on an ultra HPLC-MSMS system using an assay developed and validated by the Clinical Pharmacology Program.

5.1.1.2 Tissue

Tissue PK: Glioma tissue sampling to detect and quantify LB100 will be performed post-dose in each patient as clinically indicated (time points from end of LB100 infusion will be recorded).

The removed tissues will be rinsed with saline immediately (to remove blood that contains LB100 to avoid falsely high measurements) then divided, flash frozen, and placed in a cryo tube. Majority of the tissue will be used for PK analysis. A small aliquot (~100 ug) will be saved in cryo tube for PD evaluation. PK samples will be transported to the Laboratory of [name] (Molecular Pharmacology Section, Genitourinary Malignancies Branch) to quantitate LB100 tissue concentration.

5.1.2 Detailed PK Analysis

[figure not shown]
5.1.2.1 Overview:

LC-MS-MS assay that can measure LB-100 in human plasma treated with 50 mM NaOH. Briefly, 50 μ L of NaOH-treated plasma is extracted using a protein precipitation. Assay range is 2.0- 1000 ng/mL.

Abbreviated Title: Phase II Study LB100 gliomas

[figure not shown]
Version Date: 06/02/2022

5.1.2.2 Analyte: LB-100 (Provided by the Pharmaceutical Collaborator)

Molecular Weight: 268.1 g/mol

5.1.2.3 Internal Standard: LB-105 (Provided by the Pharmaceutical Collaborator)

Molecular Weight: 282.2 g/mol

5.1.2.4 Conditions:

HPLC: Acuity UPLC (Waters Corp, Beverly, MA)

Binary Pump

Mobile Phase A1: 5 mM Ammonium Bicarbonate (aq)

Mobile Phase B1: Methanol

Mobile Phase A2: (90/10, v/v) Water/ACN

Mobile Phase B2: ACN

Strong Needle Wash: ACN

Weak Needle Wash: 5 mM Ammonium Bicarbonate (aq)

Seal Wash: (90/10, v/v) Water/ACN

Total run time: 3 mins

Gradient elution:

Time	Flow Rate (mL/min)	%B2
Initial	0.500	2.0

Abbreviated Title: Phase II Study LB100 gliomas

Version Date: 06/02/2022

1.50	0.500	12.0
1.51	0.500	95.0
1.52	1.000	95.0
2.70	1.000	95.0
2.71	1.000	2.0
3.00	0.500	2.0

LB-100 and LB-105 retention time: 1.08 and 1.34 mins

5.1.2.5 Sample Manager

Injection volume: 5 μ l

Sample temperature: 4 °C

5.1.2.6 Column Compartment

Column: Waters Acquity UPLC BEH C18 2.1x50mm, 1.7-um particle-size

Temperature: 50 °C

5.1.2.7 Mass Spectrometer: AB Sciex Q-Trap2 5500

Source Parameters

Mode: Electrospray Positive

Curtain gas: 30

5.1.2.8 CAD: Medium

5.1.2.9 IS: 5000

GS-1: 60

GS-2: 60

Source Temperature: 650 °C

MS Tune Parameters

Compound Name	Parent (m/z)	Daughter (m/z)	DP	EP	CE	CXP
LB-100	269.1	101.0	60	10	25	12
LB-105	283.2	115.1	60	10	25	12

5.1.2.10 Master Stock Solutions

5.1.2.10.1 Master Stock Preparation – LB-100 (1 mg/mL) from the Pharmaceutical Collaborator

- a. Accurately weigh ~1-2 mg of LB-100 in a 5-mL glass centrifuge tube on the analytical balance.
- b. Add 1 mL of 10mM NaOH (aq) for each mg of LB-100.
- c. Vortex for 20 seconds.
- d. Sonicate for 15 minutes at 35 °C, to ensure all drug is dissolved.
- e. Transfer to an amber glass Waters HPLC vial and store at –80 °C.

5.1.2.10.2 Master Stock Preparation – IS (LB-105) – 1.00 mg/mL from the Pharmaceutical Collaborator

- a. Accurately weigh ~1-2 mg of LB-105 in a 5-mL glass centrifuge tube on the analytical balance.
- b. Add 1 mL of 10mM NaOH (aq) for each mg of LB-105.
- c. Vortex for 20 seconds.
- d. Sonicate for 15 minutes at 35 °C, to ensure all drug is dissolved.
- e. Transfer to an amber glass Waters HPLC vial and store at –80 °C.

5.1.2.10.3 Solution Preparation

- a. Mobile phase preparation
 - i. A1: 5 mM Ammonium Bicarbonate (aq) – Dissolve 0.395 g of ammonium bicarbonate in 1L of Milli-Q water
 - ii. A2 (Weak Wash/Seal Wash): 90:10 (v/v) Milli-Q H₂O:ACN
 - iii. B2 and Strong Wash: 100% ACN
- b. 5 N NaOH
 - i. Weigh out 20 grams of NaOH (pellets)
 - ii. Dissolve in 80 mL of H₂O (initially...) with a stir bar on a stir plate
 - iii. Once pellets dissolve and solution cools, then add 20 mL more (100 mL total volume)
- c. 50 mM NaOH in human plasma preparation
 - i. Transfer 25 mL of sodium heparin human plasma to a 50mL Falcon tube. Add 250 uL of 5 N NaOH using pipette. Mix thoroughly. Store at -20°C; the expiration date is that of the plasma
- d. 10 mM NaOH (aq), master stock diluent, preparation
 - i. Add 0.100 mL of 5N NaOH to 50 mL of DI water.
- e. 10 mM TEA (aq) stock diluent preparation
 - i. 0.5 M TEA (aq)
 1. Combine 1.4 mL of TEA and 18.6 mL of Milli-Q water in a falcon tube. Stir to mix and store the solution at room temperature. Expiration date is 1 month from preparation.
 - ii. 10 mM TEA (aq)
 1. Combine 2 mL of 0.5 M TEA (aq) and 100 mL in an approximately sized storage bottle. Stir to mix and store the solution at room temperature. The expiration date is when the 0.5 M TEA expires.
- f. 0.5% TEA in ACN, precipitation solution, preparation
 - i. Add 0.250 mL of TEA to 50 mL of ACN.
- g. 5 mM Ammonium Bicarbonate, reconstitution solution preparation
 - i. Dissolve 0.395 g of ammonium bicarbonate in 1 L of Milli-Q water. Store at room temperature. The expiration date is 1 month from preparation.
- h. Internal Standard – 200 ng/mL LB-105 in 10 mM TEA (aq)
 - i. Add 100 uL of 1 mg/mL LB-105 to 900 uL 10 mM TEA to make a 100 ug/mL solution
 - ii. Add 10 uL of 100 mg/mL LB-105 to 5 mL of 10 mM TEA (aq) to make a **200 ng/mL** IS-10mM TEA (aq) solution.
 - iii. Discard solution after use.

Abbreviated Title: Phase II Study LB100 gliomas

Version Date: 06/02/2022

5.1.2.10.4 Serial Dilutions and QC preparation

a. Pipette specified amount of stock into glass centrifuge tube. Add specified volume of diluent, 10 mM TEA (aq), by piston pipette. Vortex mix. Each stock is utilized to prepare the next dilution. Store at -20°C.

Stock Solution	Add X uL	of Stock:	Volume 10 mM TEA (aq) (uL)	Final volume (uL)	Working Stock Conc (ng/mL)	Final Conc (ng/ml)
X	100	Master	900	1,000	100,000	-
A	200	X	800	1,000	20,000	1,000
B	180	X	820	1,000	18,000	900
C	400	B	500	900	8,000	400
D	500	C	500	1000	4,000	200
E	200	D	800	1000	800	40
F	500	E	500	1000	400	20
G	250	F	750	1000	100	5
H	400	G	600	1000	40	2

5.1.2.10.5 Standard Curve

Abbreviated Title: Phase II Study LB100 gliomas

Version Date: 06/02/2022

Concentration (ng/mL)	Add x μ l	Of stock:	to 50 mM NaOH treated plasma μ l:
1,000	10	A	190
900	10	B	190
400	10	C	190
200	10	D	190
40	10	E	190
20	10	F	190
5	10	G	190
2	10	H	190

* Prepare curve in duplicate (50 μ L each), plus 50 μ L of blank human plasma for “Blank” and “IS-only” samples (in duplicate)

5.1.2.10.6 QC preparation

Prepare each QC batch by pipetting designated volume of stock solution into a 5 mL volumetric flask. Add blank human plasma until final volume is 5 mL. Mix well and aliquot 0.30 mL into clean, color-coded minifuge tubes (labeled with the date made) and store at -80 °C. (5 mL = 15 aliquots). Discard QCs older than 2 months.

QC Conc (ng/ml)	Stock	Volume Added	Actual Drug	Plasma up to-
6 (LQC; green)	F (400 ng/ml)	9 uL	3.6 ng	0.6 mL
40 (MQC; orange)	D (4,000 ng/ml)	5.0 uL	20 ng	0.5 mL
800 (HQC; red)	X (100,000 ng/ml)	4.0 uL	400 ng	0.5 mL
5,000 (DQC; blue)	X (100,000 ug/mL)	5.0 uL	500 ng	0.1 mL

* Prepare QCs in quintuplet (50 uL each). For the dilution (10-fold), add 5 uL of DQC to 45 uL of blank human plasma (in quintuplet).

5.1.2.10.7 Sample preparation

- a. Pipette 50 μ l of human plasma (standards, QCs, patient samples) into a labeled Eppendorf mini-centrifuge tube.
 - Curve in duplicate; QCs in quintuplet
- b. For patient samples and DQC samples, first add 45 μ L blank plasma, then 5 μ L of sample
- c. Add 50 μ l of 100 ng/mL LB-105 in 10 mM TEA (aq) to each calibration, QC, blank with IS, and experimental sample. *Blanks get pure 10 mM TEA
- d. Add 400 μ l of 0.5% TEA in ACN to precipitate proteins.
- e. Vortex for 30 sec to mix well.
- f. Transfer ~450 μ L into a clean, labeled 96-well Ostro plate.

- g. Push supernatent through wells using Positive Pressure Manifold at ~12-15psi for 10 min.
- h. Dry down under desiccated air in the TurboVap 96 (plate temp 40°C; gas flow ~30)
 - Once volume gets to ~100 uL remaining, add 300 uL more ACN to expedite evaporation
- i. Reconstitute with 100 µL of 5 mM Ammonium Bicarbonate (aq) directly into collection plate.
- j. Cover plate with parafilm and vortex for 20-30 sec.
- k. Centrifuge plate for 10 min at 2,000 rpm at 4 C in big centrifuge.
- l. Run on UPLC-MS/MS

[figure not shown]
5.1.2.11 Assay Validation

See Appendix **16.3**

Tissue PD effect of LB100 will be performed by assaying phospho-protein expression in glioma tissue resected prior to and after infusion of LB100.

LB100 is a serine/threonine phosphatase inhibitor. Exposure to LB100 results in increased expression of phospho-serine/threonine residues. The antibody we chose to mark LB100 activity detects variety of proteins and peptides phosphorylated at the threonine residues in a manner independent of the surrounding amino acid sequence (Cell Signaling Technology, Phospho-Threonine Antibody (P-Thr-Polyclonal), #9381). Our preclinical studies indicate that expression of phospho-protein (phospho-threonine antibody was used) upon treatment with LB100 is seen at the earliest by 4 hours (Left panel below). By 8-hours expression is reliable, and maintained for approximately 40 hours (Right panel below). Okadaic acid (OA), well-established PP2A inhibitor, was used as positive control.

Abbreviated Title: Phase II Study LB100 gliomas
Version Date: 06/02/2022

5.1.2.11.1 Planned analysis

- PK evaluations of both blood and tumor tissues will be performed in [name], and PD analyses of blood and tumor tissues in NOB Laboratory.
- A portion of blood collected for PK will be used to determine changes in phospho-protein expression in circulating PBMC.
- Intra-patient PD effect in PBMC (from above) and tumor tissue will be evaluated in all subjects for presence of correlation to identify potential predictive markers; this analysis consists of comparing PD effect in PBMC and tumor tissue to evaluate if PBMC changes predict effect in tumor tissue. Phospho-protein analyses (PD effect) of PBMC and tumor tissue will be performed in the NOB Laboratory.
- PD effect from LB100 treated tissues will only be evaluated with pathologic confirmation of recurrent tumor. Resected material demonstrating chemoradiation treatment effect or inflammatory response (pseudoprogression) will not be included in the analysis. This is because the compromised architecture of the BBB in necrotic tumor tissue may lead to falsely high penetration of LB100. These tissue PK/ PD and plasma PK specimens will be destroyed and the patient will be removed from the study.
- PK and PD specimens will be batched and performed retrospectively. The assays (both plasma and tissue) to quantitate LB100 and its major metabolite, LB100M (endothall) were developed in [name]. This data will be used to monitor LB-100 and its metabolite endothall plasma and tissue concentrations in order to correlate to pharmacodynamic endpoints, clinical response, and toxicity.
- No cell lines will be established.

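### Plasma already drawn from dosed patients with treatment-effect pathology is destroyed for a reason that applies only to tumor tissue

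*Combined protocol and SAP*

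**What the plan says.** All references are to the combined protocol and SAP.

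- **Disposal rule.** For material showing treatment effect or inflammation, section 5.1.2.11.1 states: "These tissue PK/ PD and plasma PK specimens will be destroyed and the patient will be removed from the study". The reason stands in the sentence before: "This is because the compromised architecture of the BBB in necrotic tumor tissue may lead to falsely high penetration of LB100".
- **Evaluation bar.** For the same patients, section 3.7.2 states: "PK and PD evaluations will not be performed in these subjects". It nevertheless keeps them under adverse-event follow-up, and section 6.1 carries this to Day 30.
- **Who is sampled.** Section 5.1.1.1 states: "Plasma sampling for PK measurements of LB100 will be performed on all participating subjects". It later adds: "Also, blood PK is at physician discretion".
- **Objectives.** Plasma concentrations and PK parameters of LB100 and endothall are objective 1.1.2.3. Phospho-protein change in PBMC is objective 1.1.2.4. Neither carries a pathology condition. The précis attaches the pathology requirement to treated tissues.
- **Timing and use.** Section 5.1.2.11.1 states: "PK and PD specimens will be batched and performed retrospectively". It intends to use "plasma and tissue concentrations in order to correlate to pharmacodynamic endpoints, clinical response, and toxicity".
- **PBMC source.** The same section states: "A portion of blood collected for PK will be used to determine changes in phospho-protein expression in circulating PBMC".
- **Storage.** Section 5.2.3 keeps consenting patients' samples for as long as they have scientific value.

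**The concern.** The tissue exclusion has a rationale: in necrotic tissue the barrier may be open, so finding LB100 there would say little about penetration into viable tumor. That argument does not carry over to drug in the circulation, and the documents offer no other reason for discarding plasma. The disposal rule therefore reaches further than its justification. It also sits poorly with an objective that has no pathology condition, with sampling in all participants, and with the general storage rule.

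The loss cannot be undone. With retrospective batch assay, specimens can be destroyed before anyone has measured them. What is at stake is the number of profiles behind objective 1.1.2.3, and the pairing of exposure with safety in patients who received the drug and whose adverse events are still recorded.

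**Working it through.** **1. The primary endpoint is not touched.** Section 10 continues with a response among the first 5 and declares success with at least 2 of 8. At a 40% response rate, power = 1 − 0.6⁵ − [5 × 0.4 × 0.6⁴] × 0.6³ = 1 − 0.0778 − 0.0560 = 0.866. This reproduces the stated 87%, and no plasma quantity enters it. Section 10 gives no precision figure for plasma PK that could be reproduced.

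**2. Profiles lost.** Inputs: 8 evaluable patients and up to 25 enrolled (section 10); replacement of patients with treatment effect (section 3.1). The documents give no treatment-effect rate, so let r be the assumed share of dosed patients affected. If treatment effect is the only cause of replacement and the trial reaches 8 evaluable patients (ignoring the cap of 25), the expected number lost is 8r/(1 − r).

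| r (assumed) | Expected profiles lost |
|---|---|
| 10% | 0.9 |
| 20% | 2 |
| 33% | 4 |
| 50% | 8 |

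The same share r of dosed patients would have adverse-event data without exposure data: 2 of 10, 4 of 12 and 8 of 16 in the last three rows. The figure 25 − 8 = 17 is only a ceiling.

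**3. Precision gained by keeping them.** For a log-normal AUC, the 95% confidence limits are the geometric mean divided and multiplied by exp[t(0.975, n − 1) × √ln(1 + CV²) / √n]. With CV 40% (assumption), √ln(1.16) = 0.385.

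| n | t | Factor |
|---|---|---|
| 8 | 2.365 | 1.38 |
| 10 | 2.262 | 1.32 |
| 12 | 2.201 | 1.28 |
| 16 | 2.131 | 1.23 |

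At CV 30% the factor goes from 1.28 (n = 8) to 1.17 (n = 16). At CV 50% it goes from 1.48 to 1.29.

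**4. Assay load.** Section 5.1.1.1 schedules 7 fixed plasma draws, so 2 to 8 extra profiles are 14 to 56 samples. By sections 5.1.2.10.5 and 5.1.2.10.6, a run uses 8 × 2 = 16 wells for the curve, 4 for blanks and 4 × 5 = 20 for QCs, 40 in all. That leaves 96 − 40 = 56 wells. At most one more LB100 plate is needed in single determination. Draws at tissue retrieval, duplicates and endothall would add to this.

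**5. Wording note on the plasma method.** Step b of section 5.1.2.10.7 puts 5 µL of patient sample into 45 µL of blank plasma, with no condition on concentration. The factor is (5 + 45)/5 = 10, as section 5.1.2.10.6 says for the dilution QC. Read literally, the range for patient plasma becomes 20-10,000 ng/mL. Step a takes 50 µL, and section 5.1.2.1 states 2-1000 ng/mL.

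**The case against.** The strongest reply is that the rule is a consistent design choice. Sections 3.7.2 and 5.1.2.11.1 agree with each other, affected patients are replaced under section 3.1, and plasma PK still rests on the planned 8 evaluable patients. Section 5.1.1.1 says that tissue PK is the main purpose and leaves blood PK to the physician. Tumor-to-plasma comparison needs usable tissue. Section 10 sets no precision target for plasma and no exposure-toxicity test. At r = 20% the gain is only 1.38 to 1.32; the larger gains need an assumed rate of 33-50%.

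All of this stands as a limit on severity. None of it is a reason to discard plasma already drawn from a dosed patient, and the off-study status itself comes from the tissue-based rule.

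A reader might infer more than the documents support:

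- **Bias in plasma PK.** Nothing shows that plasma kinetics differ by tumor pathology.
- **Loss of 17 profiles.** Patients may be non-evaluable for other reasons, and not every draw is certain.
- **PBMC destroyed as well.** The disposal sentence does not name PBMC. The bar on PD evaluation in 3.7.2 may cover them, but section 10 defines PD response only in tumor tissue, so this is one reading.
- **A failed planned toxicity analysis.** The link to toxicity is a general aim in 5.1.2.11.1 and is not a test in section 10.
- **A known loss of the 8 h sample through dilution.** Section 1.2.5 gives 4-6 µM only as a rough plasma level. If that were the end-of-infusion level, then with mono-exponential decay at the 1.3 h half-life (section 1.2.4) the 8 h value would be 1072-1609 × 2^(−8/1.3) = 15-23 ng/mL. With an assumed body surface area of 1.8 m², one compartment and a volume of 5-20 L, it would be 7.2-1.8 ng/mL. Late samples may fall below 20 ng/mL, but the documents do not establish the concentrations, so no size can be put on the effect. An omitted condition in step b is also plausible.

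**Conclusion.** The point holds as a cheap improvement of low-to-moderate severity. Sections 5.1.2.11.1 and 3.7.2 extend to plasma an exclusion whose only stated reason concerns tissue, and retrospective assay means that the plasma may never be measured.

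The gain is precision on a secondary descriptive objective, and exposure data for dosed patients who are followed for adverse events. Its size depends on assumed values for the treatment-effect rate and for the between-patient CV, neither of which the documents supply. The primary endpoint and its power are unaffected. The dilution step is a wording conflict to be reconciled and adds nothing to the severity.

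**What to change.** - **Sections 5.1.2.11.1 and 3.7.2:** limit destruction and PK/PD exclusion to tumor tissue, or state a reason specific to plasma.
- **Plasma:** keep and assay what has already been drawn from all dosed, consenting patients. Analyse objective 1.1.2.3 in all of them, with treatment-effect cases identified.
- **PBMC:** state whether they are kept and analysed for 1.1.2.4. Objective 1.1.2.5 needs tumor tissue and stays limited to evaluable patients.
- **Section 5.1.2.10.7:** reconcile steps a and b so that only over-range samples are diluted.

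The cost is a protocol amendment with IRB review and a check of the consent wording, which was not available for this review. On top come the plasma assays: up to about one extra LB100 plate for scheduled samples at 8 extra profiles, plus endothall, and PBMC work if PBMC are kept. No new patients or procedures are needed.

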To determine the pharmacokinetic (PK) properties of LB100 in glioma tumor tissues.

Eligibility:

- Patients with histologically proven glioblastoma and grades II-III astrocytomas and oligodendrogiomas.
- A clear clinical indication for another surgical resection must be present.
- Subjects must be \geq 18 years old.
- Karnofsky performance status of \geq 60%.
- Patients must have adequate organ function.

Abbreviated Title: Phase II Study LB100 gliomas

Version Date: 06/02/2022

Design:

- This is a two stage Phase II, open label, single institution study to determine the PK and PD profile of LB100.
- The dose (established from a Phase I study) will be 2.33 mg/m² delivered intravenously over 2 hours.
- PK and PD effect of LB100 treated tissues will only be evaluated with pathologic confirmation of recurrent tumor. Resected material demonstrating chemoradiation treatment effect or inflammatory response will not be included in the analysis.
- PK will be determined by quantitating LB100 in tumor tissues removed at various time points.
- The primary endpoint is PK response, defined as a binary variable indicating the presence/absence of LB100 in tumor tissues.
- PD effect is defined as statistically significant elevation of phospho-proteins in treated tumor tissues compared to untreated glioma specimens. Untreated inter-patient baseline variance and standard deviation (SD) will be calculated. Post-treatment PD effect difference greater than 2.5 times the baseline SD is statistically significant at the .05 significance level. Due to relatively small sample size, t-distribution is to be used to calculate the cutoff defining the PD response.
- Up to 25 patients may be enrolled to obtain 8 evaluable subjects. A two-stage design will be used. Five patients will be initially treated. If at least one of five demonstrates PK activity, 3 additional subjects will be enrolled. PK effect will be declared to be significant if at least 2 of the 8 patients demonstrate a PK response (presence of LB100 in tumor tissue).

TABLE OF CONTENTS

PRÉCIS.....	2
TABLE OF CONTENTS	4
STATEMENT OF COMPLIANCE	8
1. INTRODUCTION	9
1.1 Study Objectives	9
1.1.1 Primary Objective.....	9
1.1.2 Secondary Objectives	9
1.2 Background and Rationale.....	9
1.2.1 Glioblastoma.....	9
1.2.2 Agent to be Studied, LB100	10
1.2.3 LB100 Preclinical Studies	10
1.2.4 LB100 Phase I Study	12
1.2.5 Rationale for a Phase II Study of LB100 in Gliomas	13
2 ELIGIBILITY ASSESSMENT AND ENROLLMENT	14

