3 STUDY IMPLEMENTATION

3.1 STUDY DESIGN

This is a two stage Phase II, open label, single institution study to determine the PK and PD profile of LB100 in the setting of gliomas. Patients who are planned for craniotomy will be enrolled if they meet the inclusion criteria. Patients will be admitted to the Clinical Center for the surgery. Tumor tissue will be sampled as part of neurosurgical procedure. LB-100 will be infused over 2 hours (+/- 15 minutes) via IV infusion 2 to 4 hours before surgery. The dose established from a Phase I study will be 2.33 mg/m². Because the tumor resection phase of the craniotomy for

[figure not shown]
Abbreviated Title: Phase II Study LB100 gliomas

Version Date: 06/02/2022

recurrent gliomas typically lasts from one to 5 hours, tumor tissue will be sampled at multiple time points as clinically indicated. The exact time points of tissue removal from LB100 infusion will be recorded by a member of the study team in the OR. Plasma sampling for PK measurements of LB100 will be performed on all participating subjects. (See section **5.1**).

Up to 25 patients may be enrolled to obtain 8 evaluable patients. Five patients will be initially treated. If one of five demonstrates a PK response, 3 additional subjects will be enrolled. PK effect will be declared to be significant if at least 2 of the 8 patients demonstrate a PK response (Presence of LB100 in tumor tissue). Participants whose pathology demonstrates treatment effect or not active tumor will be replaced.

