5.1.3 Handling and Processing of Specimens

PK: The blood samples will be placed immediately on wet ice and refrigerated. The date and exact time of each blood draw should be recorded on the sample tube and the PK sheet. Tumor samples for PK and PD evaluations will be picked up from the Laboratory of Pathology by the NOB staff and transported to NOB Laboratory in Building 37. Tissues procured at various time points will be divided. Material for PD studies will be frozen in NOB Laboratory and remaining tissue for PK evaluation will be sent to the [name] Laboratory.

Please e-mail [contact] at least 24 hours before transporting samples (the Friday before is preferred).

For sample pickup, page [name].

For immediate help, call [contact] (main blood processing core number) or, if no answer, [contact] (main clinical pharmacology lab number).

For questions regarding sample processing, contact [contact].

Upon arrival in the Clinical Pharmacology Program, samples will be centrifuged and the plasma transferred into cryovials for storage at -80 C until the time of analysis. In addition, samples will be barcoded as described in Section **5.2.2.1**.

- 5.1.3.1 PD: Tumor tissues will be frozen in a -80 freezer in the NOB Laboratory until time of analysis. For PD studies on blood, PBMC will be retrieved from the [name] Laboratory.
- 5.1.3.2 Tissue blocks can be shipped to Department of Pathology at NCI at the following address:

Laboratory of Pathology
Center for Cancer Research
National Cancer Institute
[name]
[name]
Ph: [contact]

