10 STATISTICAL CONSIDERATIONS

The primary objective of this study is to determine the PK response of LB100 in glioma tissue. The PK response is defined as a binary endpoint indicating the presence/absence of LB100, and will be established by measuring the level of LB100 in resected tumor tissues. This two-stage study is designed to define a significant PK effect with an expected target PK response rate of 40% across patients. The expected 40% response rate is based on preliminary in vitro and animal studies.

Up to 25 patients may be enrolled to obtain 8 evaluable patients. Five patients will be initially treated. If one of five demonstrates a PK response, three additional subjects will be enrolled. PK effect will be declared to be significant if at least 2 of the 8 patients demonstrate a PK response. This yields 87% power to detect a 40% PK response rate across patients, with an overall 10% false positive rate under the null hypothesis that the agent has no biologic effect([17](#)).

The PK parameters, including C_{max} , AUC and elimination half-life time $t_{1/2}$, will be estimated based on standard PK modeling.

PD response is defined as statistically significant elevation of phospho-protein expression in treated tumor tissues compared to untreated glioma specimens. Tissue samples obtained with the initial surgical exposure of the tumor OR material obtained prior to LB100 infusion will be used as control. Untreated inter-patient baseline variance of phospho-protein expression and standard deviation (SD) will be calculated. Post-treatment PD effect (as measured by increase in tumor tissue phospho-protein expression) difference greater than 2.5 times the baseline SD is statistically significant at the .05 significance level. Due to relatively small sample size, t-

Abbreviated Title: Phase II Study LB100 gliomas

Version Date: 06/02/2022

distribution is to be used to calculate the cutoff defining the PD response. The frequency of PD response and its 95% confidence interval will be estimated.

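### Does batched, retrospective PK assay leave the stage 1 decision without the result it needs?

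*Combined protocol and SAP*

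**What the plan says.** The stage 1 rule appears in three places.

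- Précis, Design: "If at least one of five demonstrates PK activity, 3 additional subjects will be enrolled".
- Section 3.1: "If one of five demonstrates a PK response, 3 additional subjects will be enrolled".
- Section 10: "Five patients will be initially treated. If one of five demonstrates a PK response, three additional subjects will be enrolled".

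Section 10 defines a PK response by the LB100 level measured in resected tumor, and success as at least 2 responders among 8. It adds: "This yields 87% power to detect a 40% PK response rate across patients, with an overall 10% false positive rate".

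On laboratory timing, Section 5.1.2.11.1 says "PK and PD specimens will be batched and performed retrospectively". On logistics, Section 5.1.3 says only that "remaining tissue for PK evaluation will be sent to the" PK laboratory, with no assay date.

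Pathology decides who counts. Section 3.1 says "Participants whose pathology demonstrates treatment effect or not active tumor will be replaced", and Section 3.7.2 says of patients whose tissue shows treatment effect that "PK and PD evaluations will not be performed in these subjects".

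**The concern.** The stage 1 decision needs a tissue assay result from the first five evaluable patients. A reader who takes the timing sentence to mean one pooled run after accrual would conclude that no such result exists when the decision falls due. No section names a stage 1 batch, an assay turnaround, an accrual hold, or the person who applies the rule. Section 13.1 lists futility as a ground for stopping but does not say when the data for it arrive.

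What would be at stake is exposure. Section 12.4.2 says participants gain no direct benefit, and Section 1.2.5 says it is unknown whether LB100 crosses the human blood-brain barrier. If the rule were skipped and LB100 rarely or never reached tumor, up to three more evaluable patients, and any patients replaced along the way, would be dosed when the design would have stopped.

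**Working it through.** **Inputs.** From Section 10: 5 patients in stage 1, 3 in stage 2, success at 2 or more of 8, target rate 40%, power 87%, false-positive rate 10%. From the Précis: continue on at least 1 of 5. Section 10 gives no null rate, so it is solved for below. Detection rates of 0, 5% and 10% are assumptions. The rate of 1/3 is the share of animals in Section 1.2.5 with LB100 detected in implanted tumor (1 of 3).

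**Step 1: reproduce the stated power, with the rule operating.** Success needs either 2 or more responders in stage 1, or exactly 1 in stage 1 and at least 1 of 3 in stage 2.

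- P(0 of 5) = 0.6^5 = 0.0778
- P(1 of 5) = 5 × 0.4 × 0.6^4 = 0.2592
- P(2 or more of 5) = 1 − 0.0778 − 0.2592 = 0.6630
- P(1 or more of 3) = 1 − 0.6^3 = 0.784
- Power = 0.6630 + 0.2592 × 0.784 = 0.8663, the stated 87%

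Sections 3.1 and 10 omit the words that make the Précis version a minimum. Read literally as exactly one of five, power would be 0.2592 × 0.784 = 0.203, so a minimum of one is meant.

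**Step 2: the same design with the rule ignored.** P(2 or more of 8) = 1 − 0.6^8 − 8 × 0.4 × 0.6^7 = 1 − 0.0168 − 0.0896 = 0.8936. This does not round to 87%. The stated power therefore assumes that stage 1 is read before stage 2 opens.

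**Step 3: the null rate.** Setting the two-stage success probability to 0.10 gives a null rate of 0.0727.

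**Step 4: the cost if the rule were missed.** Expected avoidable evaluable patients = 3 × (1 − p)^5. Expected evaluable number with the rule = 5 + 3 × [1 − (1 − p)^5]; without it, 8.

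| True detection rate p | P(0 of 5) | Avoidable patients if rule missed | Expected number with rule | P(success) with rule | P(success) without rule |
|---|---|---|---|---|---|
| 0 (assumed) | 1.000 | 3.00 | 5.00 | 0 | 0 |
| 5% (assumed) | 0.774 | 2.32 | 5.68 | 5.2% | 5.7% |
| 7.27% (solved null) | 0.686 | 2.06 | 5.94 | 10.0% | 11.0% |
| 10% (assumed) | 0.590 | 1.77 | 6.23 | 17.0% | 18.7% |
| 1/3 (animal tumor data) | 0.132 | 0.40 | 7.60 | 77.1% | 80.5% |
| 40% (plan) | 0.078 | 0.23 | 7.77 | 86.6% | 89.4% |

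Replaced patients come on top; the documents give no rate from which to estimate them.

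**Step 5: set the texts side by side.**

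- The timing sentence rules out assaying each specimen as it arrives. It fixes neither the number of batches nor a date.
- The enrollment condition is itself a timing rule: three further patients may be enrolled only once a PK response is known.
- Stage 1 specimens assayed together after collection are both batched and retrospective, and they supply the result the condition needs.
- Pathology determines which tissue is evaluated (Section 3.7.2). Waiting for it is a natural reason to assay afterwards rather than in real time. The protocol's own reason for batching is not stated, so this is an inference.

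No text has to give way to another.

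**The case for a change.** The strongest case is practical. Laboratory staff working from Section 5.1.2.11.1 find no instruction to run stage 1 separately, and may naturally plan one pooled run. The enrollment condition tells the site that it needs a result; it does not tell the laboratory when to produce one. Enrolling without the result would be a deviation under Section 8.7, but that is recorded after a patient has been dosed. Low penetration is also a real possibility, since Section 1.2.5 expressly allows for a negative study, and that is the case the stage 1 rule exists to handle.

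Two parts of this stand: the stage 1 readout is implied rather than written out, and the exposure would not be trivial at low detection rates. What does not stand is the step from silence to a late result. Nothing in the protocol holds the assay until accrual ends, and a site cannot apply the enrollment condition without first asking for the assay. The larger exposure figures all assume that the site ignores a condition stated three times; the documents give no basis for a probability that it would. A sentence spelling out the sequence would do no harm, but it would alter no analysis, decision rule or operating characteristic.

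**Conclusion.** The concern does not hold as a defect in the plan. The timing sentence and the stage 1 rule are compatible, and the 87% power shows that the rule was meant to operate. Following the protocol as written gives the design that was powered. What is missing is an operational detail that the investigators must settle in order to apply their own enrollment condition. They can do so with one stage 1 batch, or sooner, because a single positive is enough to continue.

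If the rule were breached, the expected cost is 0.23 evaluable patients at the plan's 40% rate and 0.40 at the animal rate. It rises to between 1.8 and 3 at assumed rates of 10% down to 0, plus replacements. Power would rise by 2.7 points and the false-positive rate by about 1 point.

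The conclusion rests on reading the continuation rule as at least one of five, which the power figure confirms, and on the absence of any text that delays stage 1 assay to the end of the study. The 1-point figure also depends on the solved null rate of 7.27%, which the plan does not state.
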